ENCOURAGE APP – statistical analysis plan:

For the primary outcome, a one-way repeated measures ANOVA or Mann-Whitney Test will be used to examine changes in the number of breaks in sedentary time from baseline to 1-month, depending if the data are normally distributed.

Other secondary, continuous outcome measures will be analyzed with a one-way repeated measures ANOVA or Mann-Whitney Test from baseline to 1 week, 1-month, 2-month, 3-month, 4-month, 5-month, and 6-month depending if the data are normally distributed. Categorical variables will be compared using a Chi-Square test. Relationships between variables will be assessed using Pearson or Spearman correlations, as well as multivariable linear or logistic regression.

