The primary outcome for this time series quasi-experimental study is a change in moderate-vigorous physical activity within the subset of 60 participants. When doing a pre/post power analysis, an estimate of correlation between the pre and post measurements is required. We assumed a high correlation of 0.8 between measurements. Under this assumption, the sample size needed to detect a 20 minute/week increase for moderate-vigorous physical activity (Mean \pm SD; Pre: 72 \pm 64 min/week; Post: 92 \pm 86 min/week) is n=44 for with a two tailed α of 0.05 and power of 80%. Even so, we will recruit 60 participants to account for the possibility of drop out. If we assume a moderate correlation of 0.5 between Pre-Post, the sample size of 60 will still be large enough to detect a change in total physical activity (Pre: 1240 \pm 182 min/week; Post: 1402 \pm 455 min/week).

Study Data

For the experience sampling and Flurry Analytics approach to this study, data from participants at the aggregate level using the mobile App will be analyzed to categorize responses, generate frequency charts, and define themes

For the quasi-experimental design, a one-way repeated measures ANOVA or Mann-Whitney Test will be used to examine changes in breaks in sedentary time and other continuous outcome measures from baseline to 1 week, 1-month, 2-month, 3-month, 4-month, 5-month, and 6-month depending if the data are normally distributed. Categorical variables will be compared using a Chi-Square test. Relationships between variables will be assessed using Pearson or Spearman correlations, as well as multivariable linear or logistic regression.

Informed consent

The written consent form will be reviewed by the Health Research Ethics Board at the University of Manitoba prior to the initiation of the study. The consent form will describe the study procedures, risks and possible benefits, and will be reviewed by the participant prior to their enrollment in the study. Each participant will be asked to read the consent form and will be provided an opportunity to ask questions before they are enrolled. All participants will be required to provide written consent prior to initiation of study procedures. The consent form will be signed and dated by the participant and will be counter-signed by the researcher who conducted the informed consent process. The researcher will retain the original signed consent form and a copy of the form will be provided to the participant.

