One area we wish to explore is whether you take breaks from your working tasks during work hours. During a typical working day there may be opportunities to take short physical activity breaks from your working tasks. This is any interruption to your sitting time at work. For example, taking time away from your desk/workstation to move around perhaps to get a drink, have a bathroom break or even continuing a work task while standing.

How many breaks from sitting (such as standing up, or stretching or taking a short walk) during one hour of sitting would you typically take at work?
(please circle the correct answer to the following questions)

a. During a typical work day how many breaks from sitting (such as standing up, or stretching or taking a short walk) during one hour of sitting would you take at work ?	6 or more	5	4	3	2	1	0
b. What is the total time you spend in short physical activity breaks during a typical day at work?	60 minutes or more	30- 59 min	20- 29 min	10- 19 min	5-9 min	Less than 5 min	N/A

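### The non-normal fallback for change in the same people, including the SAP primary outcome, is the Mann-Whitney test, which treats baseline and follow-up as independent samples

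*SAP*

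**What the plan says.** The SAP's primary analysis opens: "For the primary outcome, a one-way repeated measures ANOVA or Mann-Whitney Test will be used". The outcome there is the change in breaks from sitting between the baseline and 1-month measurements, and the choice between the two tests turns on normality. The SAP gives secondary outcomes the same pair of tests over more occasions: "Other secondary, continuous outcome measures will be analyzed with a one-way repeated measures ANOVA or Mann-Whitney Test from baseline to 1 week", and then monthly to month 6. The protocol (Statistics, Study Data) matches: "a one-way repeated measures ANOVA or Mann-Whitney Test will be used to examine changes in breaks in sedentary time and other continuous outcome measures".

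There is one group and no control arm. Under Study procedures, the same participants answer questionnaires on 8 occasions, and the Winnipeg sub-sample wears an accelerometer on 7. Under Participant recruitment, identifiers are collected so that each person can be tracked. The Sample Size section treats the data as paired: "We assumed a high correlation of 0.8 between measurements", with 0.5 as a second case.

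For categorical data the SAP says only: "Categorical variables will be compared using a Chi-Square test". Neither document names a signed-rank, Friedman, McNemar or other test for dependent data.

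**The concern.** The two options do not answer the same question. Repeated measures ANOVA removes stable differences between people. Mann-Whitney assumes that the baseline and follow-up values come from different people, so those differences stay in its error term. When repeated values are positively correlated, its p-value is too large. It rejects less often than 5% when nothing changes and loses power when something does. A real change in the SAP primary outcome could then be reported as null because of the test alone.

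Two further points follow.

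- Mann-Whitney takes only two samples, so it cannot replace a single ANOVA across up to 8 occasions.
- If the chi-square test is meant for change over time in the same people, it has the same independence fault. The text does not say what it compares.

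The fallback could well be used. The questionnaire item on breaks (Appendix 8, Workplace Sitting Breaks Questionnaire: "How many breaks from sitting (such as standing up, or stretching or taking a short walk) during one hour of sitting") is a bounded count from 0 to a top category of six or more. The documents do not say whether the primary outcome comes from this item or from the accelerometer.

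**Working it through.** **Inputs (protocol, Sample Size).** Moderate-vigorous physical activity (MVPA): 72±64 before and 92±86 after, in min/week; correlation r = 0.8; two-tailed α = 0.05; power 80%; stated n = 44, recruiting 60. Total activity: 1240±182 to 1402±455 at r = 0.5. No such inputs are given for breaks in sedentary time.

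**The plan's own figure.** SD of change = √(64² + 86² − 2×0.8×64×86) = 51.8. A two-sided paired calculation for a 20-minute change gives n = 53 (normal approximation) or 55 (paired t), so 44 is not reproduced. That is a separate matter. At n = 60 the paired t test has 84% power. The calculation is paired, and that is what the fallback gives up.

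**Why pairing matters, in closed form.** An unpaired z statistic stands in here for Mann-Whitney, with MVPA and n = 60.

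- Unpaired standard error: √(64² + 86²)/√60 = 107.2/7.746 = 13.84. Paired, at r = 0.8: 51.8/7.746 = 6.69.
- The unpaired statistic has mean 20/13.84 = 1.445, and its true SD is 51.8/107.2 = 0.483 instead of 1.
- Power ≈ P(Z > (1.96 − 1.445)/0.483) = P(Z > 1.07) ≈ 14%.
- At r = 0.5 the SD of change is 77.4 and the ratio 0.722, so power ≈ P(Z > 0.71) ≈ 24%.
- With no change and equal SDs, the rejection rate ≈ P(|Z| > 1.96/√(1 − r)): 3.9% at r = 0.1, 2.8% at 0.2, 1.9% at 0.3, 0.6% at 0.5 and about 0.001% at 0.8.

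**Simulation of the actual tests** (20,000 trials per setting, n = 60). Normal data produce some impossible negative MVPA values, so lognormal and gamma data were also run.

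| Setting | Mann-Whitney | Signed-rank | Paired t |
|---|---|---|---|
| MVPA, r=0.8, normal | 15.7% | 81.6% | 83.3% |
| MVPA, r=0.8, lognormal | 17.1% | 95.3% | 90.7% |
| MVPA, r=0.8, gamma | 5.0% | 77.3% | 84.3% |
| MVPA, r=0.5, normal | 22.1% | 47.8% | 49.8% |
| MVPA, r=0.5, lognormal | 26.3% | 61.3% | 55.5% |
| MVPA, r=0.5, gamma | 12.4% | 41.0% | 47.8% |
| Total activity, r=0.5, normal | 72.1% | 85.9% | 87.5% |
| Total activity, r=0.5, lognormal | 42.9% | 78.6% | 90.9% |

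For gamma data, r is the correlation of the underlying normal variables. With no change, Mann-Whitney rejected 0 of 20,000 at r = 0.8, 0.4–0.8% at r = 0.5 and 1.5–2.0% at r = 0.3. The paired tests stayed at 4.5–5.1%.

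**Breaks in sedentary time (assumptions only).** If the effect is set so that a paired t test has 80% power at n = 60, Mann-Whitney has about 71% at r = 0.2, 65% at 0.3, 50% at 0.5, 22% at 0.7 and 7% at 0.8.

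The questionnaire item was also modelled as a Poisson count capped at 6, with latent r from 0.3 to 0.8:

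- n = 60, means rising by 0.3–0.4 from 1–2: Mann-Whitney 15–33%, signed-rank 40–91%.
- n = 300, the same shifts: both tests above 90%, at most about 4 points apart.
- n = 300, smaller shift from 1.5 to 1.65: Mann-Whitney 15–26%, signed-rank 39–84%.

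**The case against.** The strongest reply is that the fault is conditional and conservative. It arises only if the data are judged non-normal, it does not inflate false positives under positive correlation, and the authors may have meant the Wilcoxon signed-rank test. All of this is fair. But both documents name Mann-Whitney, an analyst following them would run it, and a pre-specified branch has to be valid when it is triggered.

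A second reply is that the largest losses come from MVPA inputs, not from breaks. If breaks come from the questionnaire, the relevant sample is nearer 300 than 60, and at the larger assumed shifts the loss almost vanishes. This stands as a limit on the illustration. It depends on the assumed effect: with the smaller shift above, the gap at n = 300 is large again. At very low correlation the conservatism is also mild, with rejection near 4% at r = 0.1.

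Third, the occasion list can be read as separate comparisons of each follow-up with baseline. Mann-Whitney could then be computed, but the pairing would still be lost.

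Finally, the chi-square point is a request for clarification, because the text does not say what is compared.

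**Conclusion.** The concern holds and should be corrected before analysis. The mismatch follows from the text alone: one group of tracked people, change over time, and an independent-samples test as the non-normal option for the SAP primary outcome and for all other continuous outcomes. On the SAP primary contrast, with two occasions, the only fault is the lost pairing. For a joint comparison over more occasions the test is also the wrong kind.

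On the protocol's MVPA inputs at n = 60, power falls from 77–95% with the signed-rank test to 5–17% at r = 0.8, and from 41–61% to 12–26% at r = 0.5. The size for breaks in sedentary time is unknown. It runs from small (low correlation, or a large effect with n near 300) to nearly all of the power (r near 0.8 with a just-detectable effect). The direction rests only on positive within-person correlation, which the sample size itself assumes. The ANOVA branch loses nothing.

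**What to change.** In both documents:

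1. Replace Mann-Whitney with the Wilcoxon signed-rank test for any two-occasion comparison, including the primary baseline to 1-month contrast. State that normality is judged on the within-person differences, and how zero differences are handled.
2. For more than two occasions, use a mixed model or GEE with robust or bootstrap standard errors. Offer Friedman only for complete cases.
3. State what the chi-square test compares. If it is the same people over time, use McNemar for two occasions or GEE logistic regression for more, and keep chi-square for comparisons between different people.
4. Name the instrument that supplies breaks in sedentary time.

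The cost is wording and slightly more analysis work; no extra data or participants are needed. There are trade-offs:

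- Signed-rank assumes roughly symmetric differences and does not test the mean change. In its standard form it drops zero differences, which were 23–52% of pairs in the capped-count settings.
- Standard GEE keeps people with missed visits but relies on data missing completely at random.
- Friedman drops anyone with a missed occasion. If 5–10% are missed independently at each follow-up (an assumption), complete cases are 0.95⁶ = 74% to 0.90⁶ = 53% over 6 follow-ups, and 0.95⁷ = 70% to 0.90⁷ = 48% over 7.
- A log transform does not avoid the problem, because it fails at zero.

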
Trial objectives and purpose

The objectives of this study are to determine if the final product ENCOURAGE App can over a 6 month period:

- 1) Enhance physical activity levels; and,
- 2) Improve cardiovascular health risk;

Trial design

The public release of the ENCOURAGE App will involve two phases (Figure 1):

- 1) The recruitment of 300 individuals through the App. Any user will be able to download the ENCOURAGE App through the iTunes Store or Google Play. Note that when participants download the App, they are not automatically enrolled in the study. Participants will be prompted, after downloading the App, with a brief description of the study, as well as a pre-screening tool will be used to determine eligibility (see below for inclusion/exclusion criteria). Users will be asked via a textbox to determine if they wish to participate in a research project. Users will be asked to participate in a *time series quasi-experimental design* study to determine if the ENCOURAGE App can support participants to increase their physical activity levels over a 6 month period. The App uses a time management technique (i.e., Pomodoro technique) as a strategy to provide prompts for users to engage in an activity. The App can be customized by the users to set prompts at intervals that fits into their schedule. For example, these activities can range from a stretching activity (e.g., a neck stretch), a standing activity (e.g., stand and read), or a physical activity (e.g., fill up the printer with paper, do a squat). Additionally, the App will use Behavior Change Techniques as a way to support participants as they reduce their sedentary behavior and improve their physical activity levels.⁷ The App uses a series of Behavior Change Techniques shown to be effective in promoting a more physically active lifestyle.^{8,9} Users will also provide feedback regarding the App using an *experience sampling approach*, which uses a list of questions to guide user feedback (**Appendix 5**). Additionally, we will use *Flurry Analytics* (<http://www.flurry.com/>) to measure, track, and analyze the ENCOURAGE App performance, and aggregate-level user activity within the App. Specifically, we wish to determine the number of user sessions within the App, frequency of use, session length, user events, technical data and errors, and user geographic distribution. For a more detailed description of the experience sampling and Flurry Analytics approaches, see **Appendix 6**.

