- 2) The recruitment of a sub-sample of 60 participants who live in Winnipeg, MB which will be drawn from the larger sample of 300 participants and by advertisement. In addition to completing all the components listed above from the recruitment of 300 participants, they will be also asked to wear a physical activity monitor, called an accelerometer.

Inclusion and exclusion criteria

Inclusion criteria:

- Male and female employees 18-70 years old
- Self-identify as being physically inactive in the last 3 months (less than 150 minutes of moderate-vigorous physical activity per week)
- Ready to adopt a more physically active lifestyle based on the Transtheoretical Model¹⁰
- Specific to the sub-sample of 60 participants: Live in Winnipeg, MB

Exclusion criteria:

- Individuals who do not have a personal mobile phone
- Any physical limitations that would not allow a person to engage in physical activity
- Any cognitive limitations that would not allow a person to consent for the study
- Specific to the sub-sample of 60 participants: Those who live outside of Winnipeg, MB.

To our knowledge, no characteristics of the participants make them especially vulnerable or require extra precautions to administer the user observation study. Participants will be healthy volunteers able to provide informed consent.

Participant recruitment

Recruitment of participants involves two phases (Figure 1):

- 1) Recruitment of 300 individuals who download the ENCOURAGE App the iTunes Store or Google play and choose to enroll in the study. Users will be asked via a textbox to determine if they wish to participate in a research project. A description of the project, as well as an electronic consent form will be provided prior to enrolment through Survey Monkey. In order to track participants in the study, we will be asking for their e-mail addresses, their date of birth, and first and last name initials.

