- 2) Recruitment of 60 individuals who live in Winnipeg, MB to wear an accelerometer. We will employ a convenience sampling approach, where participants who are already using the App and participating in the study (i.e., the 300 participants described above) will be asked to participate if they live in Winnipeg. Additionally, we will employ a convenience sampling approach at the St. Boniface Hospital, University of Manitoba, and Tactica Interactive. Participants will be contacted via e-mail. First, we will use an e-mail approach to contact participants. The e-mail approach will provide contact information for potential participants to reach research staff to facilitate the recruitment and consent of participants at a mutually agreeable location. Secondly, we will use a poster advertisement approach (**Appendix 7**) to facilitate recruitment. Posters will be placed around the St. Boniface Hospital, University of Manitoba, and Tactica Interactive. In total for the sub-study, more than 12,000 staff members at the St. Boniface Hospital, 8,700 faculty/staff, at the University of Manitoba, and Tactica Interactive will be accessible, including:
 - Nurses and Nurse Practitioners;
 - Physicians;
 - Property Management (electrical, carpentry, mechanical);
 - Administrators and clerical support staff; and,
 - Researchers
 - Software developers

Study procedures

Large study procedures:

After participants choose to participate in the study, participants will be asked to complete a series of questionnaires at baseline, one week and every month for a total of six months (i.e., 8 different

occasions). The questionnaires (**Appendix 8**) will take approximately 30-45 minutes to complete and comprise of the following:

- 1) Demographics
- 2) Depressive symptoms with the Patient Health Questionnaire-9
- 3) Physical activity using the Godin Leisure Time Exercise Questionnaire
- 4) Cardiovascular health risk using the Cardiovascular Health in Ambulatory Care Research Team (CANHEART) questionnaire
- 5) Occupational Sitting with the Occupational Sitting and Physical Activity Questionnaire
- 6) Self-efficacy levels for physical activity and reducing sedentary time with the Exercise Self-Efficacy Questionnaires and Self-Regulatory Efficacy to Manage Sedentary Behavior questionnaire
- 7) Confidence levels for reducing sedentary behaviors with the Barrier Self-Efficacy to Reduce Sedentary Behavior and Self-efficacy to Reduce Total Daily Sedentary Time questionnaires.

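### Protocol and SAP name different primary outcomes, and the only 80% power statement belongs to the one the SAP does not use

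*SAP*

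**What the plan says.** - **Protocol, Statistics, Sample Size:** "The primary outcome for this time series quasi-experimental study is a change in moderate-vigorous physical activity within the subset of 60 participants". The calculation is for a pre/post comparison with no visit named. It gives 44 as "the sample size needed to detect a 20 minute/week increase for moderate-vigorous physical activity", and recruitment is set at 60 to allow for drop-out.
- **Protocol, Statistics, Study Data:** a repeated-measures ANOVA or Mann-Whitney test "will be used to examine changes in breaks in sedentary time and other continuous outcome measures from baseline" to 1 week and to months 1 to 6. Breaks come first but are not called primary. MVPA is not named.
- **SAP, primary outcome:** the same pair of tests is used to "examine changes in the number of breaks in sedentary time from baseline to 1-month". No population or instrument is given. All other continuous outcomes are secondary.
- **Protocol, Trial objectives and purpose:** "The objectives of this study are to determine if the final product ENCOURAGE App can over a 6 month period" raise physical activity and improve cardiovascular risk. Sedentary breaks are not mentioned.

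**The concern.** The two documents disagree on the variable. Each also leaves part of its own outcome open: the protocol gives a population without a time point, and the SAP gives a time point without a population or instrument.

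This is a single-arm study with eight questionnaire occasions, seven accelerometer occasions and many scales. Prespecification is the main safeguard against picking a favourable result. As written, either outcome could be presented as primary, and nothing in the documents prevents that choice from being made after the data are seen.

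If the SAP governs, the sample-size statement no longer refers to the primary test. The 1-month contrast is also narrower than the 6-month span of the objectives.

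**Working it through.** **1. Which outcome is intended?** The texts point both ways.
- For MVPA: the Sample Size section and the first objective.
- For breaks: the SAP's label, the lead position in Study Data, the App's activity prompts (Trial design) and the recruitment poster (Appendix 7), which presents the App as reducing workplace sedentary time.
- A breaks outcome can still bear on the first objective, because the protocol lists the Workplace Sitting Breaks Questionnaire as a measure of workplace physical activity.

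**2. Which instrument would measure breaks?** There are two candidates.
- The accelerometer, worn by the 60 at baseline and monthly (Sub-study procedures).
- The Workplace Sitting Breaks Questionnaire (Appendix 8), answered by about 300. Its item is categorical, from 0 to 6 or more breaks per hour.

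Questionnaire participants "complete a series of questionnaires at baseline, one week and every month for a total of six months", so both sources exist at 1 month and the SAP's time point does not choose between them. The 1-week visit in Study Data exists only for questionnaires, but that visit list also covers all other continuous outcomes, so it does not settle the matter either.

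**3. Power for breaks.** No planning values are given, so power cannot be computed. The detectable standardized change (mean change / SD of change) can be. Paired t, noncentral t distribution, two-sided 0.05, 80% power:

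| Analysed | Detectable change |
|---|---|
| 60 | 0.37 |
| 48 (60 less an assumed 20%) | 0.41 |
| 300 | 0.16 |
| 240 (300 less an assumed 20%) | 0.18 |
| 360 | 0.15 |

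The last row covers the case where all 60 join by advertisement on top of the 300. The protocol allows this, since the sub-sample is "drawn from the larger sample of 300 participants and by advertisement". For an assumed change of 0.2, power is 33% with 60 and 93% with 300.

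**4. The protocol's MVPA figure.** Inputs from Sample Size: SD 64 (pre) and 86 (post), change 20 min/week, two-tailed 0.05, power 80%, and "We assumed a high correlation of 0.8 between measurements".
- SD of difference = √(64² + 86² − 2 × 0.8 × 64 × 86) = √2685.6 = 51.82
- Standardized change = 20 / 51.82 = 0.386
- Normal approximation: n = (1.960 + 0.842)² / 0.386² = 52.7, so 53
- Paired t: n = 55

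| Completers | Power |
|---|---|
| 44 | 70.6% |
| 54 | 79.5% |
| 55 | 80.3% |
| 60 | 83.7% |

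So 44 is not reproduced from the inputs as printed. The nearest routes to it are:
- r = 0.85: SD of difference 46.21, standardized change 0.433, power 80.1% at n = 44.
- One common SD of 75, the mean of 64 and 86, at r = 0.8: SD of difference = 75 × √0.4 = 47.43, and the two-sided normal formula gives 44.15.
- A one-sided 0.05 test at r = 0.8: 42 (normal) or 43 (t).

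The documents do not show which of these, if any, was used.

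**5. The protocol's second claim.** For total physical activity at r = 0.5: SD of difference = √(182² + 455² − 182 × 455) = 396.7, standardized change = 162 / 396.7 = 0.408, power 87.5% at n = 60. That claim is supported, but it does not concern breaks either.

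**The case against.** The contradiction itself is not in dispute. The objections concern the supporting detail.

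- **The detectable changes are paired-t values, while the SAP allows a Mann-Whitney test if data are not normal.** This stands. A repeated-measures ANOVA on two time points is equivalent to the paired t-test, but Mann-Whitney ignores the pairing. In simulated normal data at the changes detectable with 80% power (0.37 with 60, 0.16 with 300), Mann-Whitney power is roughly 65%, 50% and 6 to 8% for assumed pre-post correlations of 0.3, 0.5 and 0.8. The capped questionnaire item could well lead to that branch. The values in step 3 therefore hold only for the ANOVA branch.
- **The 44-versus-55 discrepancy is a separate matter.** It is, and it applies only if MVPA stays primary. It is included because keeping MVPA would otherwise carry a wrong number forward. The main conclusion does not depend on it.
- **The figure of 44 may reflect a simplified formula and not a mis-stated input.** This is possible, as the common-SD route shows. The text needs correcting either way.
- **The SAP read alone fixes one outcome and one visit, and precedence between the documents cannot be judged from the text supplied.** The first part is true, but the SAP still lacks a population and an instrument. On the second, neither text says it replaces the other, so uncertain precedence is itself a reason to reconcile them.
- **Six months describes the study span, not an endpoint visit.** This is fair. A 1-month contrast lies within that span, and the mismatch is a secondary point.

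**Conclusion.** The concern holds and must be fixed before analysis. The protocol and SAP name different primary outcomes, and neither defines its outcome fully. The stated 80% power attaches only to MVPA. Power for the SAP's primary test is unknown: on the paired-t (ANOVA) branch the detectable standardized change is 0.37 or 0.16, depending on whether 60 or 300 are analysed, and it would be larger under an unpaired rank test at the correlations considered.

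If MVPA is kept with the printed inputs, 55 completers are needed and 60 recruits allow 60 − 55 = 5 losses, where the stated 44 implies room for 16. The documents do not show which outcome was intended, and this review does not choose one. The 20% loss and the correlations used for Mann-Whitney are assumptions.

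**What to change.** Before analysis, set one primary outcome with its population, instrument and time point. State it identically in the protocol's Statistics section and the SAP, and make the other outcome secondary. The sponsor should choose and record the reason.

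**Option A: MVPA** (fits the Sample Size section and the first objective). Suggested text: *change in accelerometer-measured MVPA (min/week) from baseline to [time point] in the sub-study of 60, by a within-person comparison.* Six months would match the objectives. Define MVPA (intensity cut-point, valid-wear rule). Correct the sample size to 55 with the stated inputs or, if 44 was intended, state the input or formula that gives it.

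**Option B: breaks** (fits the SAP). Suggested text: *change in number of breaks in sedentary time from baseline to 1 month, measured by [accelerometer in the 60 / questionnaire in the enrolled sample], by a within-person comparison.* Align the objectives, and replace the sample-size statement with planning values or a detectable change for that variable.

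**Cost:** text changes to the protocol's Statistics section and the SAP (and to the objectives under Option B), plus an ethics amendment. No new measurements are needed, since both instruments are already scheduled at baseline and monthly to 6 months. One outcome loses primary status. Under Option A the drop-out margin shrinks to 5 of 60 if the inputs stand. Under Option B the present 80% statement can no longer be cited for the primary outcome.

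### The SAP's primary contrast for sedentary breaks stops at 1 month, which conflicts with the 6-month objectives and with the protocol's own analysis of breaks to month 6

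*SAP*

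**What the plan says.** **SAP, first paragraph.** The primary analysis examines "changes in the number of breaks in sedentary time from baseline to 1-month".

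**SAP, second paragraph.** The longer schedule, running to month 6, belongs to a different group of outcomes: "Other secondary, continuous outcome measures will be analyzed with a one-way repeated measures ANOVA or Mann-Whitney Test from baseline to 1 week, 1-month", and so on month by month. Sedentary breaks are not named there.

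**Protocol, Trial objectives and purpose.** The aim is to "determine if the final product ENCOURAGE App can over a 6 month period" do two things. The first is "Enhance physical activity levels"; the second concerns cardiovascular health risk. Neither objective mentions sedentary breaks.

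**Protocol, Statistics, Study Data.** The analysis covers "changes in breaks in sedentary time and other continuous outcome measures from baseline to 1 week, 1-month, 2-month, 3-month, 4-month, 5-month, and 6-month". Here breaks share the full schedule with the other continuous outcomes.

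**Protocol, Statistics, Sample Size.** The primary outcome is a change in moderate-vigorous physical activity (MVPA) in the sub-sample of 60. That sentence gives no time point.

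**The concern.** The primary time point fixes what the headline result can be about. The protocol asks a 6-month question, while the SAP's primary comparison ends after one month. Neither document gives a reason for choosing 1 month.

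Two things are at stake. First, the SAP followed on its own does not test its primary outcome at the trial's stated horizon, although the data for that test are collected. Second, with two documents giving different horizons for the same outcome, the choice between a 1-month and a 6-month result could be made after the data have been seen.

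**Working it through.** No arithmetic beyond counting applies. The documents give no mean, standard deviation or effect size for sedentary breaks at any time. The only sample-size calculation concerns MVPA and does not date its post measurement, so it cannot settle the time point.

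**Step 1. The sources side by side**

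| Source | Outcome | Last time point |
|---|---|---|
| Protocol, objectives | Physical activity; cardiovascular risk | 6 months |
| Protocol, Sample Size | MVPA, sub-sample of 60 (primary) | Not stated |
| Protocol, Study Data | Sedentary breaks and other continuous outcomes | 6 months |
| SAP, first paragraph | Sedentary breaks (primary) | 1 month |
| SAP, second paragraph | Other secondary continuous outcomes | 6 months |

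Rows 3 and 4 concern the same outcome and differ in horizon. Rows 1 and 4 differ in both outcome and horizon.

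**Step 2. What is collected**

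- Questionnaires, which include the Workplace Sitting Breaks Questionnaire: baseline + 1 week + 6 monthly = 8 occasions (Large study procedures).
- Accelerometer, sub-sample only: baseline + 6 monthly = 7 occasions (Sub-study procedures).

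The SAP does not say which source supplies the number of breaks. Read as a two-point comparison, its primary analysis uses 2 of 8 or 2 of 7 occasions. If the 1-week questionnaire is also meant to enter, it uses 3 of 8. On every reading, months 2 to 6 (5 occasions) are outside it.

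**Step 3. What the primary result can distinguish**

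The primary test depends only on data up to month 1. Suppose breaks rise by the same amount at month 1 in two situations: in one the rise is kept to month 6, in the other it is gone by then. The primary result is identical in both. This follows from the definition of the contrast and needs no assumption about how effects change over time.

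**Step 4. Does the problem survive once the primary outcome is settled?**

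- If breaks remain primary, the 1-month contrast still conflicts with the horizon of the objectives and with Study Data.
- If MVPA is restored as primary, breaks become secondary and would fall under the SAP's longer schedule. The primary time point is then undefined, because the protocol's primary-outcome sentence gives none.

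The SAP needs a stated primary time point either way, so outcome and time point should be reconciled together.

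**The case against.** The strongest reply is that the plan as a whole does analyse breaks to month 6, because Study Data says so and the SAP nowhere claims to override the protocol. This stands. It rules out a stronger reading that a reader might reach, namely that durability of the effect on breaks is not analysed at all. What remains is a disagreement between the documents.

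A second reply is that the 6-month objectives are not about breaks. This also stands. The objectives' own outcomes, where continuous, are still analysed to month 6 as secondary outcomes under the SAP, so fading of those effects would be visible. It does not explain why the primary contrast uses a shorter horizon than every objective.

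Third, a prespecified short-term primary can be legitimate. That is true in general, but here 1 month is neither justified nor described as short-term, and the protocol's schedule for the same outcome contradicts it.

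A reader might also infer three further things that the documents do not support:

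- That an effect lost by month 6 would count as trial success. Neither document has a success rule. The exact statement is that the primary result could be positive regardless of month 6.
- That 1 month is when the novelty of the App's prompts is greatest. Nothing in either document says this.
- That the risk can be expressed as a power figure. Any effect size for breaks would be invented, the number of participants contributing data on breaks is not stated, and the figure would show only that a real 1-month effect is usually detected at 1 month.

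**Conclusion.** The point holds as an inconsistency in the primary time point. The SAP ends its primary comparison of breaks at 1 month, the objectives run to 6 months, and the protocol analyses breaks on the full schedule. Under the SAP alone, a positive primary result carries no information about months 2 to 6.

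Its size is a matter of interpretation, not of a numerical error: five collected monthly occasions lie outside the primary comparison. The conclusion assumes that the SAP's phrase for the longer schedule excludes its own primary outcome. That is the natural reading, though the SAP does not say so outright.

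This should be fixed before analysis, but it does not invalidate the design. The data are collected and the protocol already plans to use them. It is tied to the larger conflict over which outcome is primary (MVPA in the protocol, breaks in the SAP) and should be resolved with it.

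**What to change.** In the SAP:

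1. Name sedentary breaks among the outcomes analysed at every scheduled occasion to month 6, as Study Data already does.
2. Reconcile the primary outcome with the protocol's Sample Size section. In the same change, set the primary contrast at baseline to 6 months to match the objectives.
3. Keep baseline to 1 month as a secondary contrast, and describe any result from it as short-term only.
4. Estimate the 6-month contrast from a repeated-measures model that uses all available occasions, for example a linear mixed model with occasion as a categorical effect, and not from completers alone.

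No new data collection is needed; the cost is SAP wording. The downside is that more values will probably be missing at 6 months than at 1 month. That lowers precision and, in a single-group study, could bias a completers-only pre/post comparison if those who leave differ from those who stay. The protocol recruits 60 to allow for dropout but gives no rate, so the loss cannot be sized from the documents. Item 4 reduces this problem but does not remove it.
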